## **12. EFFICACY**

No efficacy analysis is planned for this study.

### **13. SAFETY**

Safety endpoints will be analyzed using the Safety Population. Safety endpoints will be summarized descriptively as described in section 3.1.

#### **13.1 Adverse Events**

AEs will be coded using MedDRA. All AE summaries will be restricted to TEAEs only. Summary tables will include the number of participants (%) experiencing an event and the number of events. Participants will be counted only once for each SOC and PT level (categorical descriptive analysis).

The TEAE summaries will include:

- Overall summary of TEAEs.
- TEAE summary by SOC and PT.
- TEAE summary of serious events by SOC and PT.
- Drug Related TEAEs summary by SOC and PT.
- TEAE summary by SOC, PT and Maximum Severity.
- TEAE summary of events leading to study treatment withdrawal by SOC and PT.

All AEs will be listed and will include verbatim term, PT, SOC, serious adverse event (SAE), TEAE, severity, outcome, actions taken with study treatment, relationship with study treatment and discontinuation from the study. Separate listings will be created for SAEs, Drug-related AE, AEs leading to discontinuation of study drug, and AEs resulting in death. These listings will be presented by treatment group (grouping provided in section 3.7) sorted by subject ID and AE start date.

#### **13.2 Safety Laboratory Assessments**

Blood and urine samples will be collected at the time points specified in the Schedule of Events (refer to the Protocol) to conduct hematology/coagulation, chemistry and urinalysis (including microscopic examinations) analyses.

The following tests will be performed within each of the specified test panels:

Hematology:

- Basophils
- Eosinophils
- Hematocrit
- Hemoglobin
- Lymphocytes
- Monocytes
- MPV
- Neutrophils
- Platelets
- Red blood cells (erythrocytes) (RBC)
- White blood cells (leukocytes) (WBC) (total and differential)

Chemistry:

- Albumin
- Alkaline Phosphatase (ALP)

- Alanine aminotransferase (ALT)
- Aspartate aminotransferase (AST)
- Bicarbonate
- Bile acids
- Blood Urea Nitrogen (BUN)
- Corrected Calcium
- Calcium
- Chloride
- Creatinine
- Creatine phosphokinase (CPK)
- Direct Bilirubin
- Gamma-glutamyltransferase (GGT)
- High-Density Lipoprotein cholesterol (HDL-c)
- Lactate Dehydrogenase (LDH)
- Low-Density Lipoprotein cholesterol (LDL-c)
- Magnesium
- Phosphate
- Potassium
- Sodium
- Triglycerides
- Total Bilirubin
- Total Cholesterol
- Total Protein
- Urea

Urinalysis (Dipstick) & Microscopic Urinalysis:

- Bilirubin
- Blood
- Color
- Glucose
- Ketones
- Leukocytes
- Nitrite
- pH
- Protein
- Specific Gravity
- Urobilinogen

- Microscopic Examinations (listing only)

All laboratory data collected at scheduled and unscheduled visits will be included in the listings, but only results collected as scheduled visits will be included in the summary tables.

Results for individual parameters may be reported in different units depending on the analyzing laboratory. If required, the results (and the corresponding normal range cut-off values) for individual parameters may be converted to International System of Units (S.I.) to summarize the data. Parameters will be presented in both units (S.I and conventional units) in the listing.

For all the parameters where a unit value has been reported, the parameter names that will be used in the outputs will comprise of the test name and the unit of measure, for example, 'Albumin (g/L)'. For the urinalysis parameters, the parameter name will be the reported test name only. Parameters will be sorted alphabetically within tables and listings.

For all parameters where a normal range limit value was reported, the normal range will be derived based on the available lower and upper limit values and any reported mathematical symbols. If both a lower and upper limit value is available, the normal range will be presented as '(Lower, Upper)'.

The reported results for each parameter with a defined normal range will be classified ('Low', 'Normal', 'High') in relation to the defined normal range limits. If a result is equal to the normal range cut-off value, the result will be considered 'Normal'.

The hematology, chemistry and urinalysis results tables will present summary statistics for each laboratory parameter within the specific test panel. For each parameter, summaries will be presented for the baseline and each scheduled post-baseline visit. In addition, summaries will be presented for the change from baseline values at each scheduled post-baseline visit (continuous descriptive analysis).

The decimal precision to which the summaries for each parameter will be based on the maximum number of decimals to which the reported result or the normal range limits are presented to in the raw data. The results and normal ranges will be displayed to the same decimal precision in the listings.

The hematology and chemistry result with values out of normal range will present counts and percentages for the reported results at baseline and each post-baseline visit/time point. Result categories will be ordered as 'Low', 'Normal' and 'High' (categorical descriptive analysis).

Additionally, counts (%) of number participants with normal and abnormal CS/NCS at each scheduled time point will also be presented along with shift tables that will represent the changes in normal categories across post-baseline time points (categorical descriptive analysis).

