8.1.2. Subjects with Cholestatic Pruritus

To be eligible for study participation, all subjects with cholestatic pruritus must meet all the following inclusion criteria:

1. Age 18 to 80 years, inclusive
2. Has a cholestatic disorder as a result of one of the following conditions:
 - a. Diagnosis of PBC that is consistent with American Association for the Study of Liver Diseases (AASLD) (Lindor 2019) and European Association for the Study of the Liver (EASL) Practice Guidelines (EASL 2017), defined as having ≥ 2 of the following 3 diagnostic factors:
 - i. History of elevated alkaline phosphatase (ALP) levels for at least 6 months
 - ii. Positive antimitochondrial antibody (AMA) titer or if AMA is negative or low titer ($\leq 1:80$), PBC-specific antibodies (anti-GP210 and/or anti-SP100) and/or antibodies against the major M2 components (pyruvate dehydrogenase complex E2 component and 2-oxo-glutaric acid dehydrogenase complex)
 - iii. Liver biopsy consistent with PBC (collected at any time before Screening)
 - b. Diagnosis of PSC based on cholangiography at any point in time (EASL 2009, Chapman 2010)
 - c. Confirmed diagnosis of chronic hepatitis B or C virus (HBV or HCV)
3. If female, must be willing to not donate eggs from the time of informed consent until 30 days after the last dose of study drug and:
 - a. Is surgically sterile; or
 - b. Has been amenorrhoeic for ≥ 1 year and is over the age of 55 years; or
 - c. Has a negative serum pregnancy test at Screening and agrees to use a barrier method (eg, condom) during intercourse and at least 1 other acceptable contraceptive measure (eg, hormonal contraceptives, intrauterine device, vasectomized partner, or abstinence) from the time of informed consent until 30 days after the last dose of study drug
Abstinence is considered a highly effective method of birth control if the subject refrains from heterosexual intercourse from the time of informed consent until 30 days after the last dose of study drug. The reliability of sexual abstinence needs to be evaluated in relation to the duration of the study and the preferred and usual lifestyle of the subject.

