8.2.2. Subjects with Cholestatic Pruritus

All subjects with cholestatic pruritus meeting any of the following criteria will be excluded from this study:

1. Has a concomitant disease or a history of any medical condition that, in the opinion of the Investigator, could pose undue risk to the subject, impede completion of the study procedures, or would compromise the validity of the study measurements, including, but not limited to:
 - a. Presence of decompensated cirrhosis within 12 months before Screening
 - b. Presence of cirrhosis at Screening with Child-Pugh score >6, ascites or hepatic encephalopathy within 12 months of Screening, albumin of ≤ 2.8 g/dL (≤ 28 g/L), total bilirubin ≥ 3 mg/dL (≥ 51.3 $\mu\text{mol/L}$), or international normalized ratio (INR) ≥ 1.8
 - c. Presence of drug-induced cholestasis
2. Recent, current, or planned use of any new medications or adjustments to current medications within 14 days of Screening until the end of the study
3. Alanine aminotransferase (ALT) or aspartate aminotransferase (AST) $>5\times$ upper limit of normal (ULN) at Screening
4. Screening platelet count $<100,000/\mu\text{L}$
5. Screening total bilirubin ≥ 3 mg/dL (≥ 51.3 $\mu\text{mol/L}$) (total bilirubin ≥ 3 mg/dL [≥ 51.3 $\mu\text{mol/L}$] is acceptable if bilirubin is fractionated and direct bilirubin $<50\%$)
6. Positive result for HIV at Screening
7. History of malignancy of any organ system (other than localized squamous cell or basal cell carcinoma of the skin that have been excised or resolved), treated or untreated, within the past 5 years
8. Positive drug, alcohol, or cotinine screen results at Screening or Day -1
9. Significant history of abuse of drugs, solvents, or alcohol (>3 servings or units/day on average; 1 unit = 12 ounces [350 mL] of 5% alcohol beer, 5 ounces [150 mL] of 12% wine, or 1.5 ounces [45 mL] of 80 proof distilled spirits) in the past 2 years before Screening

10. Unable or unwilling to abstain from alcohol for 48 hours before Screening and from 48 hours before Day -1 until the end of the study
11. Participation in any clinical study with an investigational or approved drug/device within 30 days before Screening or is planning to participate in another clinical study while enrolled in this study (previous participation in SD-CP is allowed)
12. Allergy to any component of study drug
13. Previously participated in another dose level group in MAD-CP

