14.3.4.1.2d	Hematology Results - Out of Normal Range Values – MAD-CP/MAD-UP	Safety		×
14.3.4.1.2e	Hematology Results - Out of Normal Range Values – FE-HS	Safety		
14.3.4.1.3a	Hematology Results - Normal/Abnormal Shift Table – SAD-HS	Safety	×	×
14.3.4.1.3b	Hematology Results - Normal/Abnormal Shift Table – MAD-HS	Safety	×	×
14.3.4.1.3c	Hematology Results - Normal/Abnormal Shift Table – SD-CP/SD-UP	Safety		×
14.3.4.1.3d	Hematology Results - Normal/Abnormal Shift Table – MAD-CP/MAD-UP	Safety		×
14.3.4.1.3e	Hematology Results - Normal/Abnormal Shift Table – FE-HS	Safety		
14.3.4.2.1a	Chemistry Results - Change of Chemistry Values – SAD-HS	Safety	×	×
14.3.4.2.1b	Chemistry Results - Change of Chemistry Values – MAD-HS	Safety	×	×
14.3.4.2.1c	Chemistry Results - Change of Chemistry Values – SD-CP/SD-UP	Safety		×
14.3.4.2.1d	Chemistry Results - Change of Chemistry Values – MAD-CP/MAD-UP	Safety		×
14.3.4.2.1e	Chemistry Results - Change of Chemistry Values – FE-HS	Safety		
14.3.4.2.2a	Chemistry Results - Out of Normal Range Values – SAD-HS	Safety	×	×
14.3.4.2.2b	Chemistry Results - Out of Normal Range Values – MAD-HS	Safety	×	×

Table Number	Table Title	Population	Interim	Final
14.3.4.2.2c	Chemistry Results - Out of Normal Range Values – SD-CP/SD-UP	Safety		×
14.3.4.2.2d	Chemistry Results - Out of Normal Range Values – MAD-CP/MAD-UP	Safety		×
14.3.4.2.2e	Chemistry Results - Out of Normal Range Values – FE-HS	Safety		
14.3.4.2.3a	Chemistry Results - Normal/Abnormal Shift Table – SAD-HS	Safety	×	×
14.3.4.2.3b	Chemistry Results - Normal/Abnormal Shift Table – MAD-HS	Safety	×	×
14.3.4.2.3c	Chemistry Results - Normal/Abnormal Shift Table – SD-CP/SD-UP	Safety		×
14.3.4.2.3d	Chemistry Results - Normal/Abnormal Shift Table – MAD-CP/MAD-UP	Safety		×
14.3.4.2.3e	Chemistry Results - Normal/Abnormal Shift Table – FE-HS	Safety		
14.3.4.3.1a	Urinalysis Results - Change of Urinalysis Values – SAD-HS	Safety	×	×
14.3.4.3.1b	Urinalysis Results - Change of Urinalysis Values – MAD-HS	Safety	×	×
14.3.4.3.1c	Urinalysis Results - Change of Urinalysis Values – SD-CP/SD-UP	Safety		×
14.3.4.3.1d	Urinalysis Results - Change of Urinalysis Values – MAD-CP/MAD-UP	Safety		×
14.3.4.3.1e	Urinalysis Results - Change of Urinalysis Values – FE-HS	Safety		
14.3.4.3.2a	Urinalysis Results - Out of Normal Range Values – SAD-HS	Safety	×	×
14.3.4.3.2b	Urinalysis Results - Out of Normal Range Values – MAD-HS	Safety	×	×
14.3.4.3.2c	Urinalysis Results - Out of Normal Range Values – SD-CP/SD-UP	Safety		×

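### In the cholestatic (CP) segments the range-based chemistry tables have no gradation above normal, so worsening of a liver test already High at entry is not counted in them

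*SAP*

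**What the plan says.** SAP 13.2 sets one laboratory scheme for healthy subjects and patients. Each result with a reference range "will be classified ('Low', 'Normal', 'High') in relation to the defined normal range limits". The out-of-range table uses the same three classes: "Result categories will be ordered as 'Low', 'Normal' and 'High' (categorical descriptive analysis". The following paragraph adds "counts (%) of number participants with normal and abnormal CS/NCS at each scheduled time point will also be presented along with shift tables", described as "shift tables that will represent the changes in normal categories across post-baseline time points". SAP 18 titles the patient versions "Chemistry Results - Normal/Abnormal Shift Table – SD-CP/SD-UP" and "Chemistry Results - Normal/Abnormal Shift Table – MAD-CP/MAD-UP". In the visible text and table list there is no summary by multiple of ULN, by toxicity grade or by multiple of baseline, and none that pairs ALT/AST with bilirubin. SAP 20 assigns no figures to the CRO.

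The same section plans summaries of values and of change from baseline for every chemistry parameter. SAP 3.1 gives the statistics as n, mean, SD, median, minimum and maximum. SAP 3.2 defines change, and percent change, from each subject's own baseline. Summary tables take results from scheduled visits only (13.2). Where a test was repeated, the original result is the one tabulated (3.1).

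On entry, Protocol 8.2.2 excludes ALT or AST only above 5 × ULN at Screening. It also excludes total bilirubin of 3 mg/dL or more unless direct bilirubin is below 50%. Protocol 8.1.2 accepts chemistry expected for a cholestatic disorder. One of its three factors for primary biliary cholangitis, of which two are needed, is "History of elevated alkaline phosphatase (ALP) levels for at least 6 months".

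**The concern.** Clinical laboratory assessments are a primary safety outcome (Protocol 15.2.1, SAP 2.3.1), and Protocol 15.4 promises comparison of laboratory changes across dose levels and with placebo. In the CP segments liver chemistry is the natural focus, and it is also where subjects may start above range. A three-class scheme saturates there, because High is its top class. A reader who goes to the shift table for liver worsening by arm could see no shifts, although a subject's ALT had risen several-fold.

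**Working it through.** The plan gives no figure to reproduce here. The steps below apply its rule to assumed values inside the entry limit.

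**1. The range rule applied to ALT.** Rule: High if above 1 × ULN; a value equal to the limit is Normal (SAP 13.2). Baselines and fold rises are assumptions. The last column uses the illustrative bands ≤1, >1–3, >3–5, >5–10 and >10 × ULN.

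| Baseline (× ULN) | After 2-, 3-, 5-fold rise | SAP class | ULN band |
|---|---|---|---|
| 0.8 | 1.6, 2.4, 4.0 | Normal → High, all three | ≤1 → >1–3, >1–3, >3–5 |
| 1.5 | 3.0, 4.5, 7.5 | High → High, all three | >1–3 → >1–3, >3–5, >5–10 |
| 3.0 | 6.0, 9.0, 15.0 | High → High, all three | >1–3 → >5–10, >5–10, >10 |
| 4.9 | 9.8, 14.7, 24.5 | High → High, all three | >3–5 → >5–10, >10, >10 |

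From an abnormal baseline the SAP classes miss all 9 rises and the ULN bands register 8. The exception, 1.5 to 3.0 × ULN, is a doubling of baseline, which a table of own-baseline multiples would show.

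**2. How many subjects can show a Normal-to-High shift.** A MAD-CP level has 8 to 12 subjects at 3:1, so 6 to 9 receive EP547. SD-CP has 6, all on EP547. If a share p is already High, the number able to shift is n × (1 − p). The documents do not give p, so a range is shown.

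| p | n = 6 | n = 9 |
|---|---|---|
| 25% | 4.5 | 6.75 |
| 50% | 3.0 | 4.5 |
| 75% | 1.5 | 2.25 |
| 90% | 0.6 | 0.9 |
| 100% | 0 | 0 |

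**3. What the continuous table would show.** Take six assumed baselines of 1.5, 2, 2.5, 3, 4 and 4.9 × ULN. The last subject triples to 14.7 and the others do not change. That subject's change is 14.7 − 4.9 = 9.8. The mean change is 9.8/6 = 1.63, SD 4.00, median 0 and maximum 9.80 × ULN. The range-based shift table shows 6 of 6 High → High. So the maximum reveals the rise. It does not give the ULN multiple reached or show whether that subject's bilirubin rose as well.

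**4. Peaks off schedule.** Under SAP 3.1 and 13.2, an unscheduled result, or a repeat of a scheduled test, enters no laboratory summary table. That includes the change table in step 3. Baseline is treated differently: SAP 3.2 allows repeat and unscheduled results to define it.

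**5. CS/NCS in the shift tables.** SAP 13.4 says the ECG shift tables carry normal and abnormal NCS/CS categories. SAP 13.2 says only "shift tables that will represent the changes in normal categories across post-baseline time points" for laboratory results, under the same Normal/Abnormal title. If NCS and CS are separate levels, an NCS-to-CS change could register worsening. The text leaves this open.

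**The case against.** The case against is substantial. The plan has other routes to the same information:

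- continuous change summaries with a maximum, which with six subjects will show one large rise;
- CS/NCS counts at each scheduled time point;
- full listings with normal ranges;
- adverse events, which include clinically significant laboratory abnormalities;
- Safety Review Team evaluation of individual chemistry before escalation (Protocol 7.1, 7.3.3).

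At 6 to 9 EP547 subjects per level, reading individual data is practical, and the study tests no hypothesis.

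Much of this stands, so the worsening is not hidden. Each route has a limit, however. CS/NCS is an investigator's judgement of what is expected for the disease. Adverse-event reporting leans on the same call, since Protocol 11.1.1 keeps abnormalities judged not clinically significant out of the adverse events. The change table is in raw units and covers scheduled samples only. Listings do not summarise by arm.

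The objection also holds on the premise. Raised ALP is a history item and only one of the three factors. Primary sclerosing cholangitis and chronic hepatitis B or C qualify with no liver-enzyme threshold. An example in which every subject starts High is therefore an extreme case (the last row in step 2).

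**Conclusion.** The point holds for the CP segments. For a liver analyte already High at baseline, the range-based tables cannot register further worsening, and an off-schedule peak is absent from every laboratory summary table. How much this matters depends on the share of subjects entering High, which the documents do not give. At an assumed 25% to 100%, between 4.5 and 0 of six EP547 subjects could show a Normal-to-High shift. This is a gap in reporting with a cheap remedy. No result is lost.

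Three stronger readings are tempting, and the documents do not support them:

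- **That chemistry is classed only by range.** CS/NCS counts and continuous summaries are also planned.
- **That the change table ignores the subject's own baseline.** SAP 3.2 defines change and percent change from it, although 13.2 names only absolute change for the laboratory tables.
- **That hepatic worsening cannot be shown in the uremic segments.** Protocol 8.1.3 requires end-stage renal disease and no liver abnormality, and 8.2.3 excludes actively replicating viral hepatitis. A Normal-to-High liver shift remains visible there.

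Extending own-baseline multiples to renal analytes in the uremic segments would not help either, because they would largely follow dialysis timing. In SD-UP, dialysis on Day -1 precedes the Day 1 baseline and there is no placebo arm. In MAD-UP, the Day 1 baseline precedes that day's dialysis and the Day 2 sample follows it.

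**What to change.** In SAP 13.2 and the SAP 18 table list, for SD-CP and MAD-CP, add for ALT, AST, ALP, GGT, and total and direct bilirubin:

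1. a shift table from baseline to worst post-baseline value by ULN multiple, for example ≤1, >1–3, >3–5, >5–10 and >10;
2. counts by worst multiple of the subject's own baseline;
3. a cross-tabulation of worst ALT/AST multiple against worst total bilirubin multiple.

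State that unscheduled and repeat results count towards the worst value in these tables, as an exception to the scheduled-visit rule. State also that NCS and CS are separate levels of the laboratory shift tables, as 13.4 does for ECG. The band limits are illustrative and are for reporting only.

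All the data are already collected and study conduct does not change. The cost is SAP wording and a few extra descriptive tables, whose cells will hold small counts and should be read as such.

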### 13.3 Vital Signs

The following vital signs measurements will be taken at the time points specified in the Schedule of Events (refer to the Protocol):

- Pulse Rate (beats/min)
- Systolic blood pressure (SBP) (mmHg)
- Diastolic blood pressure (DBP) (mmHg)
- Respiratory rate (breaths/min)
- Temperature (°C)
- Oxygen Saturation (%)
- Body Weight (kg)

All vital signs data collected at scheduled and unscheduled visits will be included in the listings, but only results collected as scheduled visits will be included in the summary tables.

The parameter names that will be used in the outputs will comprise of the test name and the unit of measure, for example, 'Systolic Blood Pressure (mmHg)'. Parameters will be sorted in the order that the measurements were collected in on the Vital Signs eCRF page within the tables and listings.

Vital signs measurements will present summary statistics for the results at the baseline and each scheduled post-baseline visit for each of the parameters. In addition, summaries will be presented for the change from baseline values at each scheduled post-baseline visit (continuous descriptive analysis).

The decimal precision to which the summaries for each parameter will be presented will be based on the maximum number of decimals to which the results were reported on the eCRF.

### **13.4 12-Lead Electrocardiogram (ECG)**

The following ECG measurements will be taken at the time points specified in the Schedule of Events (refer to the Protocol):

- Ventricular Rate (beats/min)
- PR Interval (msec)
- QT Interval (msec)
- QTcF Interval (msec)
- QRS Duration (msec)
- Overall Clinical Interpretation Finding

All ECG data collected at scheduled and unscheduled visits will be included in the listings, but only results collected as scheduled visits will be included in the summary tables.

The parameter names that will be used in the outputs will comprise of the test name and the unit of measure, for example, 'Ventricular Rate (beats/min)'. Parameters will be sorted in the order that the measurements were collected in on the ECG eCRF page within the tables and listings.

ECG measurements will present summary statistics for the results at the baseline and each scheduled post-baseline visit for each of the parameters. In addition, summaries will be presented for the change from baseline values at each scheduled post-baseline visit (continuous descriptive analysis).

The decimal precision for each parameter will be based on the maximum number of decimals to which the results were reported on the eCRF.

The summary of overall ECG interpretation findings table will present counts and percentages along with shift tables that will represent the changes in normal and abnormal NCS/CS categories across post-baseline time points (categorical descriptive analysis).

